Gemtuzumab ozogamicin (GO) [Mylotarg®] is an antibody-drug conjugate used for the treatment of AML patients with myeloid cells that express the CD33 receptor.¹⁰ The FDA approved GO for the treatment of newly diagnosed CD-33-positive AML in September 2017.¹ for use alone or in combination with chemotherapy, depending on the characteristics of the patient. In April 2018, GO received marketing authorisation from the EMA for the European Union, to be used in combination with daunorubicin and cytarabine chemotherapy.^{11,12} The ALFA-0701 multicentre Phase 3 trial results demonstrated the effectiveness of GO, which ultimately led to its approval. Patients aged 50-70 years old with newly-diagnosed de novo AML were treated with GO in combination with daunorubicin and cytarabine chemotherapy. The trial demonstrated an estimated median event-free survival (EFS) of 17.3 and 9.5 months for patients receiving GO and chemotherapy or chemotherapy alone respectively and 27.5 and 21.8 months for overall survival (OS).¹

Over the years GO has been studied in multiple different combination regimens and different dosing schemes.¹² There is limited knowledge of its real-world use and outcomes as first line treatment with the recent licensed dosing (ie, 3 doses during the induction cycle). Using results from a feasibility study conducted by Adelphi Real World (ARW) and contacts with data source custodians, evidence suggests that 1L treatment with GO has been used to treat AML patients in several countries. Pfizer would like to conduct a study investigating the treatment patterns and effectiveness outcomes of 1L GO use on de novo AML patients in real-world healthcare, specifically those in the favourable and intermediate risk groups. This will allow the assessment of whether GO prescription patterns are aligned with licensed dosing/guidelines and will provide novel insights into whether the observed real-world outcomes associated with these prescription patterns are effective. The study will use a combination of AML specific data sources and a retrospective medical chart review using a Case Report Form (CRF) to conduct a multi-country study with Belgium and Austria. Such data sources were identified during a feasibility assessment and were deemed to likely capture a sufficient sample size of patients (according to the eligibility criteria outlined in [Section 9.2](#)).

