Each data source is likely to capture a large proportion of GO-treated patients in that country, hence their selection. The Austrian, Belgian and German centres have been selected as they meet the feasibility requirements (capture the relevant data variables) and due to the sample size of GO patients that they contain. The Austrian Myeloid Registry recruits data on patients with myeloid diseases from 15 Austrian centres (excluding the Medical University of Vienna) with an estimated enrollment of 3000 patients. The eligibility criteria below are largely based upon the recommend use of GO; ensuring that the overall patient sample gathered will be clinically representative of the GO treated population.

The initiation date of 1L treatment within the indexing period will be defined as the index date. De novo AML diagnosis will be captured within the screening questions of the eCRF and fully defined for each data source within the Statistical Analysis Plan (SAP). Baseline patient demographics and clinical characteristics will be evaluated at index. Treatment patterns and effectiveness outcomes will be described throughout the follow-up period. Patients will have a minimum follow-up of 3 months defined as patients with 3 months of data, following the 1L treatment initiation. This will allow for assessment of treatment patterns and early effectiveness outcomes. Follow-up will end with the following endpoints: death, loss of data (eg, transfer to a new hospital) or end of the study period. In order to maximise the follow-up data captured necessary to accurately assess survival outcomes (EFS, RFS and OS), follow-up will extend up until either the last data available for the patient (in Austrian, Belgium, and German sites), or the date of database extraction (in the Austrian Myeloid Registry). Patients who have limited follow-up data which is not sufficient for the assessment of OS and accurate EFS and RFS, will be right-censored for the purpose of survival outcome specific analysis. Patients who die within the 3-month follow-up period would be considered eligible for inclusion in order to evaluate EFS, RFS and OS outcomes.

Figure 1. Study Schematic

Study Schematic–eCRF and secondary data dataset design

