9.3.2. Outcomes

9.3.2.1. Treatment Patterns

The treatment landscape for GO will be described for all de novo AML patients treated with the drug as a 1L therapy. The following will be assessed to describe the overall treatment pathway for each patient:

Pharmacological treatment

- **Lines of therapy (LoT):** The number of LoT received by a patient from and including the index date, to the end of their observation period will be reported as a categorical (1, 2) numeric variable
- **Treatment regimen:** The number and percentage of patients receiving a given treatment regimen will be reported for each LoT, up to 2 LoT – defined as the combination of drugs (including GO)
- **Treatment setting pathway:** The treatment setting by regimen will be reported as a categorical variable using the following groups:
 - Induction, consolidation

The number of patients receiving GO in induction **AND** consolidation (in succession) will also be reported.

- **Number of doses per regimen:** The number of doses of GO in the first-line treatment regimen, broken out by first-line induction and first-line consolidation. This will be reported as a categorical (1, 2, 3, 4+) numeric variable.
- **Dosing per administration:** Actual total dose (mg) administered for GO will be reported for the first-line treatment regimen, broken out by first-line induction and first-line consolidation. This will be reported as a categorical (1, 2, 3, 4+) numeric variable.
- **Time between dosing:** Time in days between the combined chemotherapy and GO initiation (and vice versa) and time in days between each GO dose will be reported as continuous numerical variables. *Subject to availability – as multiple doses of GO are captured as one regimen; this information may not be explicitly available.*
- **Cytogenetic complete response:** Recorded for each LoT as a categorical variable:
 - Yes, No, Not examined, Undisclosed

Stem cell transplants

- **Stem cell transplants:** The occurrence of a haematopoietic stem cell transplant (HPSCT) [allogeneic or autologous] will be reported as a binary categorical variable – ‘Y’ or ‘N.’ The type of transplant will not be reported.

The feasibility of capturing/defining these data points will be assessed upon communication with data custodians and sites. Details of variable definitions will be captured in the SAP.

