9.3.2.2. Effectiveness Outcomes

- **Patient response to treatment regimen:** Response to each treatment regimen will be recorded as a categorical variable:
 - CR; CR with incomplete platelet recovery (CRp); CR with incomplete haematologic recovery (CRi); Partial Remission; Stable Disease; Progressive Disease; Uncertain Response; Other (before evaluation); Not evaluated/unknown

The response to stem cell transplant for relevant patients will be reported separately, again as a categorical variable:

- CR; CRp; CRi; Partial Remission; Stable Disease; Progressive Disease; Uncertain Response; Not evaluated/unknown

The event of veno-occlusive disease (VOD) following stem cell transplant for relevant patients will be recorded as a binary ‘Y’ or ‘N’ variable, where available.

The event of graft versus host disease (GvHD) following stem cell transplant for relevant patients will be recorded as a binary ‘Y’ or ‘N’ variable, where available.

- **Time to subsequent treatment:** Time in days between start of 1L induction treatment and the initiation of the next line of treatment will be reported as a continuous numerical variable.
- **MRD status:** Minimal residual disease status will be reported for each treatment regimen as a categorical variable:
 - Positive, negative, unknown
- **EFS:** Defined as the date of the start of induction treatment for de novo AML to relapse, death from any cause, or failure to achieve any of the following: CR; CRp; CRi
- **RFS:** Defined as the date of the start of first line treatment for de novo AML, to relapse, will be reported as a separate outcome specifically.

- **OS:** Defined as the date of the start of first line treatment for de novo AML, to death from any cause.

Detailed methodology for identifying the effectiveness outcomes of interest will be built in collaboration with the Pfizer team and aligned as closely with ELN 2017 guidelines⁷ were possible, whilst recognising the limitations associated with identifying complex outcomes using routinely collected real-world data. As such, sensitivity analyses will be applied where necessary, with full details to be documented in the SAP.

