9.9. Limitations of the Research Methods

Study design limitations:

- The overall sample size of patients (~230) may limit comparisons if subgroup numbers are low, such as ELN risk status (intermediate and favourable) and cytogenetic risk subgroups. However, the sample size is not substantially low in relation to the global population of interest. Furthermore, this is purely a descriptive study with no statistical comparisons and so the assessment of treatment patterns and effectiveness outcomes will not be affected by the small sample sizes.
- As this a multi-county multisource study, it is likely that there will differences in data variable availability. To mitigate this, the eCRF used for Austrian, Belgian, and German sites will be designed using knowledge of datasets known to collect data from medical records. When requesting data from the Austrian Myeloid Registry, variables will be requested in this same format where possible. Furthermore, during analysis where specific variables or outcomes cannot be assessed/described in one data source, subgroup analyses could be conducted for a subset of patients from certain data sources.
- GO-based treatment regimens and dosing schedules may differ through the different countries, adding to the complexity of the assessment of effectiveness outcomes. Subgroup analyses could be conducted for subsets of patients receiving the same or similar treatment regimens and or dosage schedules. Furthermore, dosing information per regimen may not be available in the data sources. For example, a total dose of GO may be provided, without numbers and/or timings. Nevertheless, number of doses is likely to be imputable due to prescribing guidelines and consistent quantities of GO supplied in vials (each dose). Timings of doses could be derived algorithmically, details of which would be provided in the SAP.
- The multiple cytogenetic risk groups included in the study cohorts, could similarly add complexity to the assessment of effectiveness outcomes. As a result, the analyses could include a stratification of risk group, subject to sample sizes.

- The minimum follow-up period has been set to 3 months. Consequently, for a large number of patients, OS and EFS maybe not assessable. These patients will be censored for such analyses.

Data source related limitations:

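### If the optional subgroups by GO schedule received are applied to EFS and OS timed from treatment start, the longer-treated group (chiefly GO in consolidation) looks better even with no GO effect

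*Protocol*

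**What the plan says.** Section 7 gives as one purpose of the study to learn "whether the observed real-world outcomes associated with these prescription patterns are effective". Section 9.9 then says that GO regimens and dosing schedules may differ between countries, "adding to the complexity of the assessment of effectiveness outcomes", and offers this response: "Subgroup analyses could be conducted for subsets of patients receiving the same or similar treatment regimens and or dosage schedules".

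The clocks are set in section 9.3.2.2:

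- EFS: "Defined as the date of the start of induction treatment for de novo AML to relapse, death from any cause", with failure to reach CR, CRp or CRi as a further event.
- OS: "Defined as the date of the start of first line treatment for de novo AML, to death from any cause".
- RFS: "Defined as the date of the start of first line treatment for de novo AML, to relapse". Death and non-response are not RFS events.

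Section 9.2 sets the index: "The initiation date of 1L treatment within the indexing period will be defined as the index date". Because inclusion criterion 4 requires GO in first-line induction, the three clocks in effect start on the same day.

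The treatment patterns in section 9.3.2.1 include the number of GO doses (1, 2, 3, 4+), split by induction and consolidation, and a count that begins "The number of patients receiving GO in induction" and goes on to require consolidation as well. Section 7 describes consolidation as following response to induction. Patients who die within 3 months stay in the cohort (sections 9.2 and 9.2.1).

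**The concern.** Whether a patient received GO in consolidation is not known at index. To be counted in that group, the patient must have survived induction and will normally have responded. Early deaths and non-responders are therefore left in the induction-only group, while the clock for both groups starts at induction. The time before consolidation is event-free by definition in one group and not in the other (immortal time). For EFS there is also selection on response, because non-response is itself an event.

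A Kaplan-Meier plot drawn this way would show longer EFS and OS with more GO whatever the drug does. Given the purpose stated in section 7, outcome by GO pattern is a contrast that readers will look for. Having no hypothesis test does not help, since the curves themselves misdescribe the groups they name.

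Section 9.9 discusses selection bias, missing data and data lag, but says nothing about groups formed by treatment after index. Annex 2, item 7.3, which lists time-related bias among its examples of information bias, is ticked as addressed and points to the limitations section.

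**Working it through.** **The plan's own figure.** The only quantity that can be reproduced is the expected sample size: 50 + 30 + 50 + 42 + 18 + 40 = 230, as stated. The protocol gives no expected remission rate and no expected share receiving consolidation GO, so the sizes below rest on assumptions.

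**EFS, consolidation GO against the rest, no true effect.** Let *c* be the proportion reaching remission and *s* the share of remitters given GO in consolidation. Assume that all consolidation-GO patients are remitters, that induction failures have their EFS event before consolidation, and that post-remission time is exponential with median 24 months, counted from month 2.

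- Failure share in the consolidation-GO group: 0.
- Failure share in the other group: (1 − c)/(1 − c·s).
- Event-free from month 2 to month 12: exp(−ln 2 × 10/24) = 0.749.
- 12-month EFS: 0.749 against (1 − failure share) × 0.749. Spurious gap: failure share × 0.749.

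| c | s | Failure share, other group | 12-month EFS, consolidation GO vs other | Gap (points) |
|---|---|---|---|---|
| 0.8 | 0.5 | 0.20/0.60 = 0.333 | 75% vs 50% | 25 |
| 0.9 | 0.3 | 0.10/0.73 = 0.137 | 75% vs 65% | 10 |
| 0.7 | 0.7 | 0.30/0.51 = 0.588 | 75% vs 31% | 44 |

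The last two rows are the extremes over c = 0.7 to 0.9 and s = 0.3 to 0.7.

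**OS, no true effect.** Take the median OS of 27.5 months that section 7 quotes for the GO arm of the cited phase 3 trial, with exponential times. Suppose a proportion *p* is planned for the longer schedule and a patient joins that group only if alive at the qualifying dose at time L.

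- Longer-treated group: median = L + 27.5. With L = 2 months this is 29.5.
- Other group, for t beyond L: S(t) × (1 − p)/(1 − p·S(L)). With L = 2 and p = 0.5, S(2) = 0.951 and the denominator is 0.525. The median is where S(t) = 0.525, so t = 27.5 × log2(1/0.525) = 25.6 months.
- At 12 months under the same assumptions: about 78% against 70%.

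This OS model includes only the need to be alive at the qualifying dose. It does not link non-response to earlier death.

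**Induction dose counts.** With the same model and L = 7 days, median OS is 27.7 months against 27.3 (p = 0.5) or 26.6 (p = 0.8). Using the cited median EFS of 17.3 months, EFS is 17.5 against 17.1 or 16.4. In simulation, the apparent rate ratios were 0.96 to 0.99.

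**Check of the remedy.** In the same simulation, with 1,000,000 patients, no true effect and L from 7 days to 4 months, restricting to patients event-free at L and counting time from L brought the rate ratio back to between 0.99 and 1.00. With 10-30% induction failures added, EFS 12 months after the landmark was about 62% in both groups.

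**The case against.** The strongest reply is that the protocol does not commit to this analysis. The sentence in section 9.9 says only that subgroups could be run. It names no endpoint, no time origin and no split by consolidation GO. Section 9.3.2.1 lists dose counts and consolidation use as treatment patterns, not as strata for survival. Annex 2, item 10.4, answers No on stratified analyses. Section 9.7 leaves detailed methods to the SAP, which is not shown and may include a landmark.

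Much of this stands. A reader might infer that the protocol plans EFS and OS curves by GO schedule; it only permits them. The point remains because the protocol itself supplies both parts, the grouping by treatment received and the clock from treatment start, and offers the grouping specifically for effectiveness outcomes. Used together as written, they give a wrong answer.

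Four wider readings are also tempting and not supported:

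- That every grouping by regimen is biased. Section 9.3.2.1 defines a regimen as a drug combination, and one fixed at the start creates no immortal time.
- That every early death or induction failure falls among those with fewer doses. Section 7 places the licensed doses within the induction cycle, so a patient can receive all of them and still fail.
- That RFS is affected in the same way. As defined, it counts relapse only, so early death and non-response are not events, and no RFS artefact has been shown.
- That the tick at Annex 2, item 7.3, is a specific claim to have dealt with immortal time. The item covers information bias in general, with time-related bias as one example.

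**Conclusion.** The concern holds in a limited form. If the optional subgroups in section 9.9 are formed by GO treatment known only after index, and EFS and OS keep the time origins of section 9.3.2.2, the longer-treated group is favoured with no GO effect. The main case is GO in induction plus consolidation against induction only.

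The direction follows from the definitions. The size depends on assumptions outside the protocol: about 10 to 44 points in 12-month EFS for 70-90% remission, 30-70% of remitters given consolidation GO and a post-remission median of 24 months, and about 4 months in median OS (29.5 against 25.6) for a qualifying dose at month 2 with half the patients planned for it. Much of the EFS gap is selection on response.

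Whole-cohort curves and groups known at index are unaffected. This is worth correcting before analysis, but it is not a flaw in any analysis to which the protocol is committed.

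**What to change.** In sections 9.7 and 9.9, state that EFS and OS will not be shown from index by treatment received later, and say what will be done instead:

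- **GO in consolidation:** start the clock at consolidation start, or at a fixed landmark, among patients alive and in CR, CRp or CRi; or treat consolidation GO as a time-dependent exposure.
- **Number of GO doses:** use a fixed landmark after the induction dosing window, among patients alive and event-free, where dates allow.
- **From-index curves:** keep them for the whole cohort and for groups known at index, such as risk group, age and the chemotherapy combination started at index.

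Add a sentence on immortal time to section 9.9, so that the Annex 2 answer on information bias is backed by the text.

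The cost is a few sentences and a little programming. Landmark subsets will be smaller than the full cohort of about 230, with wider intervals. Some dose dates may be missing, since section 9.3.2.1 makes dose timing subject to availability and section 9.9 warns that only a total dose may be recorded. Patients who cannot be classified by the landmark should be counted and reported.

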8. RESEARCH QUESTION AND OBJECTIVES

This study aims to answer the following research question:

How is GO being used in real world clinical practice of de novo intermediate/favourable risk AML patients and what are the outcomes?

Co-Primary objectives

- To describe the patient demographics and clinical characteristics of patients treated with GO in intermediate and favourable cytogenetic risk, de novo AML.
- To describe GO treatment patterns in the study population, including:
 - Combination chemotherapy regimen
 - GO use in induction and consolidation
 - Number of doses of GO
 - Timing of GO doses in 1L treatment
 - GO dosage

Secondary objective

- To describe 1L treatment effectiveness outcomes for the study population, including:
 - Time-to-next treatment
 - Survival (EFS, RFS, OS)

Exploratory objective

- To describe MRD (minimal residual disease) status for the study population.

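### Deriving the number of GO doses partly from prescribing guidelines pulls a co-primary description towards the benchmark it is meant to be compared with

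*Protocol*

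**What the plan says.** **The objective.** Protocol section 8 lists "Number of doses of GO" and the timing of doses under the co-primary treatment-pattern objective. Section 9.3.2.1 defines the variable as "The number of doses of GO in the first-line treatment regimen, broken out by first-line induction and first-line consolidation", in categories 1, 2, 3 and 4+.

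**The purpose.** Section 7, on what the study is for: "This will allow the assessment of whether GO prescription patterns are aligned with licensed dosing/guidelines". The Abstract repeats this. Section 7 describes the benchmark as the "recent licensed dosing (ie, 3 doses during the induction cycle").

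**The data problem.** Section 9.3.2.1 warns about time between doses: "as multiple doses of GO are captured as one regimen; this information may not be explicitly available". Section 9.9 adds that "a total dose of GO may be provided, without numbers and/or timings".

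**The proposed remedy.** Section 9.9 says that the "number of doses is likely to be imputable due to prescribing guidelines and consistent quantities of GO supplied in vials (each dose"). On timing: "Timings of doses could be derived algorithmically, details of which would be provided in the SAP".

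**The general rule.** Section 9.7 reports missing values as an unknown category or as a number missing. It allows imputation, where missingness is large or differs between important groups, as a sensitivity analysis.

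**The concern.** The guideline appears twice. It is the benchmark for describing observed practice, and it is part of the rule that would create the observation where dose-level records are lacking. To the extent that a count rests on the guideline, it cannot serve as independent evidence on whether the guideline was followed.

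At stake is the distribution of dose counts, one of the main descriptive results. If derived and recorded counts are shown together unmarked, a reader cannot tell how much apparent agreement with licensed dosing was recorded and how much was assumed. Section 9.9 itself expects dosing schedules to differ between countries, which weakens the case for one conversion rule across sources.

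**Working it through.** **1. What the conversion needs.** Let T be the recorded total and a the assumed amount per dose. The derived count is T / a. T is data; a is not. Section 9.9 offers two sources for a: the prescribing guideline, or one standard vial quantity per dose.

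**2. What it can and cannot show.** In units of a, purely as algebra:
- T = 3a is coded as 3 doses. Two doses of 1.5a (2 × 1.5a = 3a) or four of 0.75a (4 × 0.75a = 3a) give the same total and the same code, so these departures are hidden.
- T = a is coded as 1 dose. A total well away from the expected one therefore still shows as different, although one cannot tell whether the number or the size of the doses differed.
- T = 4a over the whole first line could be 3 in induction and 1 in consolidation, or 2 and 2. Section 9.3.2.1 requires this split. A total alone cannot supply it, so a schedule must be assumed.

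**3. Whether other text contains the problem.** Section 9.7 would place imputation in a sensitivity analysis. Section 9.9 offers the derivation as a way round the missing information. It does not refer to that rule, ask for derived counts to be flagged, or keep them out of the alignment assessment. Only the timing algorithm is referred to the SAP; the basis for the count is stated in the protocol.

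**4. Who could be affected.** The Table 1 estimates (section 9.5) sum to the stated total: 50 + 30 + 50 + 42 + 18 + 40 = 230. Section 9.3 says the eCRF captures all variables of interest, while the registry's variables are not explicitly known. If the whole registry, and only the registry, needed derivation (an assumption), the share is m = 30 / 230 = 13.0%.

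**5. Upper bound on the shift.** Let p be the true share following licensed dosing, assumed equal in derived and recorded patients. If every derived patient were coded as aligned:

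reported share = p(1 − m) + m = p + m(1 − p), so the shift is m(1 − p).

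With m = 13.0% and p assumed:

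| Assumed true p | Reported, at most | Shift (points) |
|---|---|---|
| 50% | 56.5% | 6.5 |
| 60% | 65.2% | 5.2 |
| 70% | 73.9% | 3.9 |
| 80% | 82.6% | 2.6 |
| 90% | 91.3% | 1.3 |

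For scale, the 95% CI half-width at p = 60% and N = 230 is 1.96 × √(0.6 × 0.4 / 230) = 6.3 points. If chart-review sites also needed derivation, each further 10% of patients would add at most 0.10 × 0.40 = 4 points at p = 60%.

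**The case against.** The strongest reply is that the count would come from a recorded total and vial quantities as well as from guidelines, so it can fall in any of the four categories. That stands. A reader might infer that every derived patient is simply given the guideline pattern and that no departure could be detected. The text does not support this, and the formula above is therefore a ceiling.

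Section 9.9 is also a limitations section in conditional wording, and section 9.7 already has a sound rule for missing data. A reader might infer that imputed counts will enter the main table as if observed, with a CI that is too narrow. The protocol does not say so. It also does not exclude it, because section 9.9 is not tied to section 9.7.

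Three further points stand in part:
- The timing algorithm is left to the SAP, which is not at hand, and nothing says it would use guideline intervals. It cannot be called circular on this evidence.
- No endpoint defines a proportion aligned; alignment is a stated use of the results. The share in the calculation is an illustration of that use.
- The problem may be small. Section 9.3 thinks the registry probably holds the listed variables, and section 9.4 says it extracts data much as an eCRF does. Against this, section 9.9 refers to the data sources in general and accepts that charts may lack intended variables.

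None of this removes the narrower point: the guideline is named as part of the basis for a variable that is meant to inform guideline alignment, without a safeguard where it is named.

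**Conclusion.** The point holds in this limited form. Using guideline assumptions to turn a total into a dose count, and to split it by treatment phase, pulls derived counts towards the guideline pattern and can hide departures that leave a similar total. Section 9.9 does not confine such counts to the role that section 9.7 gives to imputation.

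The size is unknown, because the documents do not say how many patients will lack dose-level records. With the registry alone affected (13%), a true share of 60% in derived and recorded patients alike, and every derived patient coded as aligned, the reported figure would be at most about 65%. All three conditions are assumptions, and the last is deliberately extreme. Larger affected shares have no source in the protocol, so larger distortions should not be claimed.

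**What to change.** Amend section 9.9, with a cross-reference to section 9.7, so that:
- the main description of dose count and between-dose intervals uses recorded values only, with unrecorded values shown as unknown by data source;
- any derived count or timing is flagged, reported only in a sensitivity analysis, and kept out of any statement on alignment with licensed dosing;
- dose-level administration data are requested from the registry in the eCRF format, which sections 9.6 and 9.9 already foresee for registry variables.

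Bounds that treat all unknown patients first as aligned and then as not aligned would be a useful but optional addition.

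The cost is a wording change, one flag in the dataset, and a denominator for dose count that may fall below 230 (to about 200 if the whole registry lacked dose-level records). The share among recorded patients is then free of this distortion, but represents the whole cohort only if missing records are unrelated to the number of doses; the display by source helps a reader judge that.
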